10.1 Definition of adverse events and reporting requirements

10.1.1 Adverse events

An adverse event (AE) is any untoward medical occurrence (e.g., any unfavorable and unintended sign [including abnormal laboratory findings], symptom or disease) in a subject or clinical investigation subject after providing written informed consent for participation in the study. Therefore, an AE may or may not be temporally or causally associated with the use of a medicinal (investigational) product.

The investigator has the responsibility for managing the safety of individual subject and identifying adverse events.

Novartis qualified medical personnel will be readily available to advise on trial related medical questions or problems.

The occurrence of adverse events must be sought by non-directive questioning of the subject at each visit during the study. Adverse events also may be detected when they are volunteered by the subject during or between visits or through physical examination findings, laboratory test findings, or other assessments.

Adverse events must be recorded in the Adverse Events CRF under the signs, symptoms or diagnosis associated with them, accompanied by the following information (as far as possible) (if the event is serious refer to [Section 10.1.2](#)):

1. its severity grade
 - mild: usually transient in nature and generally not interfering with normal activities
 - moderate: sufficiently discomforting to interfere with normal activities
 - severe: prevents normal activities
2. its relationship to the study treatment. If the event is due to lack of efficacy or progression of underlying illness (i.e. progression of the study indication) the assessment of causality will usually be 'Not suspected'. The rationale for this guidance is that the symptoms of a lack of efficacy or progression of underlying illness are not caused by the trial drug, they happen in spite of its administration and/or both lack of efficacy and progression of

underlying disease can only be evaluated meaningfully by an analysis of cohorts, not on a single subject

3. its duration (start and end dates) or if the event is ongoing, an outcome of not recovered/not resolved must be reported.
4. whether it constitutes a SAE (see [Section 10.1.2](#) for definition of SAE) and which seriousness criteria have been met
5. action taken regarding with study treatment. All adverse events must be treated appropriately. Treatment may include one or more of the following:

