 - Dose not changed
 - Dose Reduced/increased
 - Drug interrupted/withdrawn
6. its outcome:
 - a. not recovered/not resolved
 - b. recovered/resolved
 - c. recovering/resolving
 - d. recovered/resolved with sequelae
 - e. fatal, or unknown

Conditions that were already present at the time of informed consent should be recorded in medical history of the subject.

Adverse events (including lab abnormalities that constitute AEs) should be described using a diagnosis whenever possible, rather than individual underlying signs and symptoms.

Adverse event monitoring should be continued for at least 30 days following the last dose of study treatment.

Once an adverse event is detected, it must be followed until its resolution or until it is judged to be permanent (e.g. Continuing at the end of the study), and assessment must be made at each visit (or more frequently, if necessary) of any changes in severity, the suspected relationship to the interventions required to treat it, and the outcome.

Information about adverse drug reactions for the investigational drug can be found in the Investigator Brochure (IB).

Abnormal laboratory values or test results constitute adverse events only if they fulfill at least one of the following criteria:

- they induce clinical signs or symptoms
- they are considered clinically significant
- they require therapy

Clinically significant abnormal laboratory values or test results must be identified through a review of values outside of normal ranges/clinically notable ranges, significant changes from baseline or the previous visit, or values which are considered to be non-typical in subjects with the underlying disease.

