12.5.2 Safety endpoints

For all safety analyses, the full analysis set will be used.

Commercially Confidential Information

Safety summaries (tables, figures) include only data from the on-treatment period with the exception of baseline data which will also be summarized where appropriate (e.g., when change from baseline is used). In addition, a separate summary for any deaths including on treatment and post treatment deaths will be provided. In particular, summary tables for adverse events (AE) will summarize only on-treatment events.

The on-treatment period lasts from the date of first administration of study treatment to 30 days after the date of the last actual administration of any study treatment.

Adverse events

All information obtained on adverse events will be displayed as described above taking into account the study design involving sequences,

Commercially Confidential Information

Listings will be down to patient level. The number (and percentage) of patients with treatment

emergent adverse events (events starting after the first dose of study medication or events present prior to start of double-blind treatment but increased in severity based on preferred term) will be summarized in the following ways:

- by treatment dose group including split by first and second four weeks in second period, primary system organ class and preferred term.

Commercially Confidential Information

Separate summaries will be provided for study medication related adverse events, death, serious adverse events, other significant adverse events leading to study and/or investigational drug discontinuation and any adverse events leading to dose adjustment.

A subject with multiple adverse events within a primary system organ class is only counted once towards the total of the primary system organ class. Adverse events which will be counted for a specific treatment period are those which are treatment-emergent. These events are those with an onset after the start of the dose level treatment period, or which were present prior to the start of the treatment period but increased in severity, changed from being not suspected to being suspected of study drug relationship, or developed into SAEs after the start of the dosing period.

Vital signs

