### **Adverse events**

All information obtained on adverse events will be displayed as described in [Section 4](#) taking into account the study design involving sequence.

The number and percentage of subjects with adverse events will be tabulated by body system and preferred term with a breakdown by dose for each period separately.

An adverse event starting in one period and continuing into the next period is counted only in the onset period. A subject with multiple adverse events within a body system and treatment period is only counted once towards the total of this body system and treatment.

Separate summaries will be provided for study medication related adverse events, death, serious adverse events, other significant adverse events leading to study and/or investigational drug discontinuation and any adverse events leading to dose adjustment.

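### SAP 8.2 counts a carried-over adverse event only in its onset period, whereas protocol 12.5.2 also counts it in a later dose period if it worsens, becomes suspected or becomes serious there

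*SAP*

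**What the plan says.** SAP 8.2, under Adverse events, tabulates patients with adverse events by body system and preferred term, broken down by dose separately for each period. Its rule for an event that crosses a period boundary is one sentence: "An adverse event starting in one period and continuing into the next period is counted only in the onset period". The visible text attaches no condition to it.

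Protocol 12.5.2 sets its own rule for the same count: "Adverse events which will be counted for a specific treatment period are those which are treatment-emergent". Events with onset after the dose-level period has started qualify. So do events "which were present prior to the start of the treatment period but increased in severity", and events that "changed from being not suspected to being suspected of study drug relationship, or developed into SAEs after the start of the dosing period".

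SAP 1.1 describes the SAP as implementing the analysis planned in the protocol. SAP 1.4 gives the first dose of the assigned sequence in Period 1 (4 weeks) and the second dose in Period 2 (8 weeks), with at least 10 patients randomized 1:1 to two sequences.

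**The concern.** The two documents give different counting rules for the same table. They agree on an event that runs unchanged from one period into the next: it belongs to its onset period. They disagree on the three changes that the protocol names.

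The period boundary is also the change from the first to the second dose in the sequence. An event that was mild on the first dose and becomes severe, suspected or serious on the second is information that a table by dose and period should show. Under the SAP sentence it stays with the first dose only. The discrepancy has one direction: for events that start on treatment, a Period 2 cell under the SAP rule can equal the protocol cell or fall below it, but never exceed it. In cells of 5 or 10 patients, one patient is visible in the percentages.

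**Working it through.** The plan states no figure for this count, so there is nothing to reproduce. The check compares the two rules case by case and then works out the size of the difference.

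**Step 1. The rules side by side, for an event that starts in Period 1**

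| What happens in Period 2 | Counted in Period 2 under SAP 8.2 | Counted in Period 2 under protocol 12.5.2 |
|---|---|---|
| Continues unchanged | No | No |
| Becomes more severe | No | Yes |
| Becomes suspected to be drug-related | No | Yes |
| Becomes an SAE | No | Yes |
| Change entered as a new record with a start date in Period 2 | Yes | Yes |

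Both rules count the event in Period 1, so the onset-period cell is the same.

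**Step 2. Inputs**

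- n = number of patients in the Period 2 cell. SAP 1.4 gives at least 10 patients randomized 1:1, so 10/2 = 5 per sequence. The doses are redacted, so both n = 5 and n = 10 are shown.
- a = patients with an event in that row that starts in Period 2.
- c = patients with no such event whose carried-over event, held as one record, became more severe, suspected or serious in Period 2.

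The documents give no event frequencies, so the values of a and c below are illustrative assumptions.

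**Step 3. Formulas**

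- SAP cell: a/n
- Protocol cell: (a + c)/n
- Difference: c/n

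**Step 4. Results**

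| n | a | c | SAP | Protocol | Difference |
|---|---|---|---|---|---|
| 10 | 2 | 1 | 2/10 = 20% | 3/10 = 30% | 10 points |
| 5 | 1 | 1 | 1/5 = 20% | 2/5 = 40% | 20 points |

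If the change is entered as a new record, that patient moves from c to a. In the first example both rules then give 3/10 = 30%, a difference of 0. The difference is also 0 if the patient already has another event counted in that row and period, because SAP 8.2 counts a patient once per body system and period.

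**The case against.** **Redaction.** SAP Section 4 is almost wholly redacted, and so is some adverse event text in protocol 12.5.2. The SAP uses the term treatment-emergent without a visible definition, and one may stand in Section 4. This stands as a limit: the finding concerns the visible wording. It does not remove the conflict. For these summaries SAP 8.2 refers to Section 4 for how events are displayed, while the counting sentence is explicit and exclusive. An exception elsewhere would contradict that sentence, which would still need editing.

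**Data entry.** If sites enter a worsening as a new record, the rules agree. That also stands. The visible text does not require it, and protocol 10.1.1 describes following a detected event to resolution, where "assessment must be made at each visit (or more frequently, if necessary) of any changes in severity". That fits a single record at least as well.

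**Nothing is lost.** The event is still counted in its onset period, and the protocol states "Listings will be down to patient level". SAP 8.2 also plans separate summaries of drug-related and serious events. This is correct and confines the effect to the summary tables. It does not correct the Period 2 cell, and the visible text does not say which period the separate summaries would use for such an event.

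**Onset-only counting is a legitimate convention.** It is, if declared. Here the SAP claims to implement the protocol and visibly declares no change.

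A reader might infer two stronger points that the documents do not support:

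- *The SAP also mishandles events that start before the first dose.* Adverse events are collected "in a subject or clinical investigation subject after providing written informed consent for participation in the study", so such events can exist. But the SAP sentence does not address them, and the lack of a visible rule proves little when Section 4 is redacted. The protocol is also not settled here: its overall definition covers "events present prior to start of double-blind treatment but increased in severity based on preferred term", whereas its per-period rule adds causality and seriousness.
- *All adverse event tables should change, including those for public disclosure.* The disclosure tables have their own rule for counting consecutive events, and their summary by dose and period is referred to Section 4. The conflict shown here does not extend to them.

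**Conclusion.** The SAP is wrong as written, with minor severity. Its sentence contradicts the protocol's per-period rule for carried-over events that worsen, become suspected or become serious.

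Followed literally, it can understate incidence at the second dose by one patient for each patient who meets all three conditions: the event changed in one of those ways in Period 2, it is held as a single record, and the patient has no other event counted in that row and period. Each such patient is 10 points at n = 10 or 20 points at n = 5.

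How often this will happen cannot be judged from the documents. The conclusion assumes that no redacted text overrides the visible sentence. It makes no claim about events that start before dosing or about the disclosure tables, and gives no size for Period 3. The study is non-confirmatory and these tables are descriptive, so the effect is on how clearly the safety summaries show change after the second dose starts.

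**What to change.** In SAP 8.2, replace the sentence with the protocol's per-period rule, limited to events that start on treatment and carry over. Suggested wording:

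*An adverse event that starts on treatment in one period and continues into the next is counted in its onset period. It is also counted in the later period if, after the start of that period, it increased in severity, became suspected to be related to study drug, or became an SAE. If it continues unchanged, it is counted in the onset period only.*

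Apply this to the SAP 8.2 adverse event summaries by dose and period, and leave the disclosure occurrence rule as it is. If the sponsor prefers onset-only counting, the SAP should declare and justify the departure from protocol 12.5.2.

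Before database lock, confirm that the date of each change can be derived from the adverse event data, or that changes are entered as new records. Protocol 10.1.1 requires changes in severity to be assessed at each visit, but the visible text does not say that each change is stored with a date.

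The cost is one SAP sentence, plus minor programming if those dates can be derived. If they cannot, the protocol rule may not be programmable for single-record events, and the SAP should say so.

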### **Adverse event reporting for Clinical Trial Safety Disclosure (CTSD)**

For the legal requirements of ClinicalTrials.gov and EudraCT, two required tables, 1) on treatment-emergent adverse events which are not serious adverse events with an incidence greater than 5% and 2) on treatment-emergent serious adverse events and SAE suspected to be related to study treatment, will be provided by SOC and PT on the full analysis set population. These tables will be produced by Novartis. The value of the cutoff value X will be decided with the team when disclosure tables are prepared.

The summary will be done by dose and Period as described in [Section 4](#).

If for a same patient, several consecutive AEs (irrespective of study treatment causality, seriousness and severity) occurred with the same SOC and PT:

- a single occurrence will be counted if there is  $\leq$  1-day gap between the end date of the preceding AE and the start date of the consecutive AE
- more than one occurrence will be counted if there is  $>$  1-day gap between the end date of the preceding AE and the start date of the consecutive AE.

For occurrence, the presence of at least one SAE / SAE suspected to be related to study treatment / non-SAE has to be checked in a block e.g., among AE's in a  $\leq$  1-day gap block, if at least one SAE is occurring, then one occurrence is calculated for that SAE.

The number of deaths resulting from SAEs suspected to be related to study treatment and SAEs irrespective of study treatment relationship will be provided by SOC and PT.

Adverse events of special interest (AESI) definitions are found in the compound electronic Case Retrieval Strategy (eCRS). Treatment-emergent AESIs (based on the latest eCRS at the time of DBL) will be summarized by frequency and percentage of patients by risk name, MedDRA preferred term and by treatment sequence. A listing of the case retrieval strategy will be presented.

## **Exposure**

Duration of exposure will be presented graphically, using a horizontal bar chart with subjects as the y-axis and the number of days exposed to LNP023 as the x-axis.

## **Other safety evaluations**

Commercially Confidential Information

### **8.3 Graphical presentation**

Individual overlaid profile plots over time will be used to visualize trends in longitudinal safety data (vitals, ECG, lab parameters) with current dose level per patient color-coded will be presented.

## **9 Pharmacokinetic / pharmacodynamic relationships**

Commercially Confidential Information

Commercially Confidential Information

Commercially Confidential Information
